#### Sample size considerations

We will power our study to detect a 10 Gy difference in mean radiation doses between tumors with local control and 6 months vs those which progressed. Based on preliminary data, we expect that the standard deviation of doses will be 12Gy, and that approximately 60% of tumors will retain local control at 6 months. We will use a two-sided test with type I error of 0.05. In preliminary data, within-patient correlation was 0.6-0.7, and we saw an average of 2 tumors per patient. We therefore will enroll 43 patients in this study to have approximately 80% power to detect a difference of 10 Gy.

It is anticipated that 10 patients will be recruited for Day 1 PET-CT studies. This number of patients would be expected to detect a difference in the range of 12-20 Gy (Day 0 – Decay-adjusted day 1). Although we may not get a significant result, the point estimates may give an indication of whether the microspheres are moving. This level of certainty is felt to be appropriate for an exploratory aim.

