## **4.5 Patient Registration Procedure**

Patients will be consented at the time when the decision to pursue radioembolization is made. No protocol-specific workup will take place prior to obtaining informed

consent. However, at this time it will be determined that the patient has had a complete staging workup within the last 4 weeks including:

- Diagnostic imaging of the abdomen utilizing either CT with contrast, MRI, or PET/CT
- Complete metabolic panel (CMP)
- Complete blood count (CBC)
- Coagulation studies (PT, INR)

Eligible patients will be entered on study centrally by the Fox Chase Cancer Center QA Coordinator or their designee. Following registration, participants must begin protocol related treatments and evaluations within 14 days of registration. If a participant does not receive protocol therapy following registration, the participant will be recorded as withdrawn from study and will be replaced. The QA Coordinator must be notified of cancellations and withdraws as soon as possible.

Participants may be registered from 9:00 am to 5:00 pm excluding holidays and weekends by calling the QA Coordinator at [contact]. The site's investigator or designee will then fax the completed registration form, entire, complete and signed informed consent document and HIPAA authorization documents and the completed eligibility checklist to [contact]. The QA Coordinator or designee will notify the site's investigator or their designee by email when participant registration is confirmed and the sequence number has been assigned. Participants must be registered and have received a sequence number assigned by the QA Coordinator prior to the initiation of treatment.

Exceptions to the current registration policies will not be permitted.

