### **Follow-up Visits**

Participants will be followed for 5 years or until death, whichever comes first. Follow-up visits will be scheduled at 1 week, 1 month, 3 months, and then every 3 months for one year, every 6 months for 1 year and then annually for 3 years or death whichever comes first

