### **Additional Radioembolization Treatments**

As a part of standard of care, many patients will require a second radioembolization.

Patients requiring a second radioembolization treatment will be scanned additionally at Visit 1 (Day 0) and Visit 2 (Day 1) after the second treatment.

Visit 2 of the second radioembolization will take place on Day 1, and will be pursued in only a subset of patients. This will include only a PET-CT for the purposes of determining the stability of microsphere placement. The Visit 2, Day 1 PET-CT should be scheduled 24 hours +/- 3 hours after the Visit 1, Day 0 post-treatment PET-CT.

In these cases the 1 month follow up visit may be conducted on the day of the second treatment.

Follow up visits may be conducted by any investigator and will include the following studies:

- CBC and CMP will be drawn at each follow-up visit
- Beginning at the 3-month visit, each visit should be accompanied by tumor imaging to evaluate local control. The modality of tumor imaging will be at the discretion of the investigator, but it is encouraged to use the same modality consistently over time.

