## 8.0 Statistical Considerations

In this study, we will evaluate the dosages received by tumors and surrounding tissue using PET-CT data. The primary objective is to determine the relationship between radiation dose to 70% of the tumor volume and local control at 6 months. We will conduct this analysis at the tumor level, as different tumors may receive different doses of radiation, and may have different progression statuses at 6 months. We will use standard summary measures such as means, medians, ranges, and standard deviations to characterize the dosages received by tumor and other tissue. We will use percentages and frequency tables to evaluate other characteristics such as tumor histology, number of liver tumors per patient, and volume of liver tumors.

We will determine the relationship between radiation dose and local control at 6 months using regression models with Generalized Estimating Equations (GEE) to account for within-patient correlation. We will use logistic regression to adjust for potentially confounding factors such as tumor volume, primary histology, and SIR-Spheres versus Therasphere intervention. We will also determine the relationship between radiation dose to healthy tissue, and side effects such as fatigue, nausea, pain and elevated liver function tests. Each

side effect will be characterized as present or absent, and we will test the relationship between radiation dose to the relevant type of healthy tissue and each side effect. For example, we will look at the relationship between dose to the normal liver and elevation of liver function tests.

In further secondary analyses, we will explore the relationship between the distribution of activity measured by PET-CT, and the distribution predicted by T-99m labeled MAA. This can be translated into predicted dose. We will calculate differences between PET-CT and MAA doses, and present the data graphically. We will use the method proposed by Bland & Altman (2007) to assess the agreement between the two methods. Finally, in a subset of patients, we will explore the change in dose measured by PET-CT scan between day 0 and day 1. The dose at day 1 will be adjusted to account for the decay of the yttrium-90 using  $A=A_0e^{-(0.693t/T_{1/2})}$ . Observed changes in dose may be due to microsphere migration, and our main interest is to look for a systematic change in dose received based on this migration.

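### Does Section 8 need a stated rule for tumours that have neither progressed nor been scanned at 6 months?

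*Combined protocol and SAP*

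**What the plan says.** Section 2.1 makes the primary objective the relationship between dose to 70% of the tumour volume and local control at 6 months. Section 8.0 analyses this by tumour: "We will determine the relationship between radiation dose and local control at 6 months using regression models with Generalized Estimating Equations (GEE". The sample size section powers the study for a "10 Gy difference in mean radiation doses between tumors with local control and 6 months vs those which progressed". It assumes about 60% of tumours controlled, states "we expect that the standard deviation of doses will be 12Gy" and "We will use a two-sided test with type I error of 0.05", takes a within-patient correlation of 0.6–0.7 with two tumours per patient on average, and concludes "We therefore will enroll 43 patients in this study to have approximately 80% power to detect a difference of 10 Gy".

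Three other places bear on tumours without a 6-month status:

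- Section 5.0, Follow-up Visits: "Participants will be followed for 5 years or until death, whichever comes first".
- Section 5.0, in the list of follow-up studies: "Beginning at the 3-month visit, each visit should be accompanied by tumor imaging to evaluate local control".
- Section 4.5, the only replacement rule: "If a participant does not receive protocol therapy following registration, the participant will be recorded as withdrawn from study and will be replaced". It does not cover patients lost after treatment.

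No section states how to code a tumour with neither documented progression nor a 6-month scan, and none gives an expected loss rate.

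**The concern.** The power calculation puts every tumour of the 43 patients in one of two groups. Patients with liver metastases or primary liver cancer and performance status up to 2 may die or miss imaging before 6 months, so some tumours may fit neither group. Three codings are conceivable: leave such tumours out, count them as not controlled, or count them as controlled.

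These codings do not estimate the same quantity, even when loss is unrelated to dose and outcome. Counting lost tumours as not controlled mixes non-progressed tumours into the progressed group and dilutes the dose difference. If the coding were chosen after seeing the results, the 5% type I error would also be exposed. On this view the primary estimate, and not only its precision, rests on a decision the plan has not recorded.

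**Working it through.** **Inputs from the sample size section.** Difference 10 Gy; SD 12 Gy, read as within group; 60% controlled; two-sided α 0.05; within-patient correlation (ICC) 0.6–0.7; 2 tumours per patient; 43 patients, so 86 tumours.

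**The plan's own figure.** Independent tumours needed: (1.96 + 0.84)² × 12² / (10² × 0.6 × 0.4) = 47.1. Multiplying by the design effect 1 + ICC and dividing by 2 gives 37.7 patients at ICC 0.6 and 40.0 at 0.7, or 38 and 41 rounded up. The noncentral-t version gives 40 and 42. With 43 patients, power is 83–85% (normal) or 81–84% (t). The claim of about 80% is reproduced.

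**Implied odds ratio.** For two normal groups with a common SD, the log odds ratio per Gy is 10/12². Per 10 Gy the odds ratio is exp(10 × 10/144) = exp(0.694) = 2.00.

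**Effect of each coding.** Assume a share L of patients is lost at random, and a share q of the progressing tumours in those patients was documented before loss. Both are assumptions. The logistic slope was refitted to the resulting population.

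- *Left out, documented progressions kept.* Selection depends on outcome but not on dose, so the logistic slope and the 10 Gy difference are unchanged.
- *Counted as not controlled.* Difference = 10 × 0.4/(0.4 + 0.6L).
- *Counted as controlled.* Difference = 10 × 0.6/(0.6 + 0.4L(1 − q)); with q = 0.5 the denominator is 0.6 + 0.2L.

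| Loss L | Left out: OR per 10 Gy | Not controlled: difference, OR | Controlled (q = 0.5): difference, OR |
|---|---|---|---|
| 10% | 2.00 | 8.70 Gy, 1.79 | 9.68 Gy, 1.94 |
| 20% | 2.00 | 7.69 Gy, 1.65 | 9.38 Gy, 1.89 |
| 30% | 2.00 | 6.90 Gy, 1.55 | 9.09 Gy, 1.84 |

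With no loss the three coincide. If all the loss falls on tumours that would have progressed, leaving out and counting as not controlled both give 2.00, and the contrast between them disappears.

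**Which coding the text supports.** The comparison group consists of tumours that progressed, and Section 8.0 describes the tumour-level outcome as progression status at 6 months. A tumour seen to progress at the 3-month scan belongs in that group whether or not a later scan exists. A tumour never seen to progress does not belong there. Without a 6-month scan it is not known to be controlled either. It therefore has no outcome, and the logistic GEE omits it. Death has its own place in the plan: overall survival is a separate secondary objective in Section 2.2. Counting death as failure would change the endpoint to being alive with local control, which the plan does not describe.

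**Cost of leaving out.** With q = 0.5, the number of tumours omitted is 86 × (0.6L + 0.2L), about 7 at 10% loss and 14 at 20%. The t-based power at ICC 0.7 and 0.6 is 78% and 81% at 10% loss, 75% and 77% at 20%, and 71% and 73% at 30%.

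**The case for a change.** The strongest reply is that software drops only what someone has coded as missing. How a death before 6 months is coded is a human decision, and counting it as failure is a familiar choice. In simulated trials of this design the three codings disagreed on p < 0.05 in 16–21% of trials at 10% loss and 29–33% at 20%. Under the null, taking the best of the three gave 6–7% and 7–8% false positives respectively, while each coding alone gave 4–5%.

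It stands that the plan is silent and that a written rule would remove doubt. The figures have less force. They treat three codings as equal candidates when the text favours one, and the inflated error needs the most favourable result to be picked after the fact, which nothing in the documents suggests.

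Leaving out is not proof against every kind of loss. When the odds of loss were halved per 10 Gy of patient mean dose (20% loss, q = 0.5), the log odds ratio was 0.758 left out and 0.746 not controlled, against a true 0.694. When the odds were doubled, it was 0.639 left out and 0.724 controlled. In each scenario another coding came slightly closer. Across the two scenarios, leaving out has the narrowest range of odds ratios: 1.89–2.13, against 1.29–2.11 for not controlled and 1.68–2.06 for controlled.

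The plan also names no working correlation. With an exchangeable structure at 20% random loss, the odds ratios were 2.11–2.21 left out and 1.82–1.89 not controlled. The gap between codings persists, but it does not make the second coding the plan's.

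**Conclusion.** No change is called for. This is a missing detail that the wording of Section 8 lets an analyst fill sensibly: documented progression by 6 months counts as progressed, a 6-month scan without progression counts as controlled, and a tumour with neither is omitted. On that reading the odds ratio stays at 2.00 per 10 Gy when neither loss nor the early documentation of progression depends on dose. The stated power is not in dispute, and at 10% loss it remains close to 80%.

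The drop to 1.65 requires three things together: a 20% loss that the documents do not give, loss unrelated to dose and outcome, and a coding that the text disfavours. A sentence recording the rule and a window for the 6-month scan, with the two other codings as sensitivity analyses, would be a reasonable courtesy to readers. In a single-arm registry study it would record what the analysis already implies and would not alter the primary result.

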## 9.0 Administrative

This study will be conducted in accordance with local, state and Federal regulations and according to accepted good clinical practice guidelines.

### 9.1 Data Reporting

The FCCC Study Monitor will request case report form submission upon resolution of outstanding queries. Participating sites are responsible to respond to queries prior to the next scheduled monitoring visit. Participating sites are responsible for submitting case report forms to the QA Specialist / Study Monitor within two weeks of request.

The QA Coordinator is responsible for compiling and submitting data to the study PI and statistician on an ongoing basis for monitoring as described in the data safety monitoring plan and reporting to the Extramural Data and Safety Monitoring Committee.

All patient information will be stored on an electronic Microsoft Office Excel Spreadsheet on a drive accessible only to the study team members for the purpose of entering, reviewing and analyzing data. Any paper records, such as case report files, produced will be stored in locked file cabinets with limited access.

The CTO Regulatory Coordinator is responsible for distributing and tracking review of all IND Action Letters, Safety Reports, study specific Serious Adverse Events

## **9.2 Retention of Records**

Time points for the retention of records are described in detail in the contract between the grantor and the CTO and passed on to the participating site. Please refer to the study specific terms for specific time points. In all cases the QA Specialist / Study Monitor must be notified of any plans to move records to an offsite location prior to doing so.

## **9.3 Informed Consent**

The IRB approved informed consent documents must be signed by the patient, or the patient's legally authorized representative, before his or her participation in the study. The case history for each patient shall document that informed consent was obtained prior to participation in the study. A copy of the informed consent documents must be provided to the patient or the patient's legally authorized representative. If applicable, they will be provided in a certified translation of the local language.

Original signed consent forms must be filed in each patient's study file or medical record with a copy in the study file.

## **APPENDIX I**

### **Tc-99m MAA scan protocol**

**Purpose:** To assess arterial perfusion of the liver and the fraction of radiopharmaceutical tracer that will pass through the liver and lodge in the lungs.

**Agent:** Technitium-99m labelled MAA (Macro-aggregated Albumin)

**Dose:** 150- 200 MBq

**Equipment:** Any large FOV gamma camera

**Administration:** The patient needs to have a trans-femoral catheter placed in the hepatic artery. The Technitium-99 labelled MAA is injected through the catheter into the hepatic artery by a qualified physician.

**Imaging:** The patient is positioned supine under the gamma camera and the images recorded.

Analogue:

- Anterior and posterior images of abdomen and thorax. Measure 700k -1000k cts for abdomen and equivalent time for thorax.
- Right lateral Abdo - same time acquisition as for Anterior.

Digital:

- 4 frames; 300"/ frame. 64 x 64 matrix Word mode.
- Image anterior and posterior abdomen
- Image anterior and posterior thorax

**Analysis:** Draw ROI around whole of liver and whole of lung fields. Calculate G mean for liver region and lung region.  
Calculate Lung/liver ratio

**Interpretation:** If lung/liver ratio is >10% then there is need for dose reduction of SIR-Spheres

### **SPECT protocol:**

**SPECT acquisition:** 360 arc, using a body-contoured elliptic orbit, optimally obtaining 120 (minimum of 60) projections at 15–25 s per projection (every 3–6\_angle), depending on the number of projections and sensitivity of the detector. The SPECT acquisition takes, on average, approximately 25 min. The images are acquired into a 128 x128 (16-bit) matrix, corrected for attenuation, and reconstructed using a 2-dimensional orderedsubset expectation maximization iterative technique (at least 10 subsets and 2 iterations are typical, but the number may vary according to the manufacturer).

**Processing:** A 3-dimensional postprocessing filter, which should be specified in detail by the manufacturer (e.g., the Hanning postprocessing filter with a cutoff frequency of 0.85 cycles/cm) is typically applied to the SPECT dataset.

## **APPENDIX II**

### PET/CT scan protocol

**Purpose:** To assess the treatment dose distribution, and potential calculation of dosimetry of Y-90 Sir-Spheres and/or Theraspheres.

**Instrumentation:** PET/CT scanner (Siemens Biograph 16 in Fox Chase Cancer Center)

**Posttherapy Imaging:** Within 5 hours after the administration of Sirsphere and/or Theraspheres, a PET/CT scan will be performed covering the liver area in order to verify localization of the Sirsphere/Therasphere in the targeted tumor. A proof of concept for such a technique has been reported (3).

**Parameters:** The patient will be positioned on the PET/CT scanner with arms raised up, and a localization scout scan will be performed in the abdominal region. A two-bed PET/CT acquisition will be set up centered on the liver. A low dose CT scan will be performed followed by a 10 minute per bed PET acquisition. The PET data will be reconstructed using manufacturer recommended procedure, and the data will be analyzed to determine the hepatic localization of microspheres.

**For Subset of patients:** Diagnostic (intravenous contrast) CT should be performed immediately after the PET scan without moving the participant, using portovenous phase for optimal visualization of the liver. The volume of IV contrast is per institution standard.
